3.1.2 Stage II

Participants (those identified as the person to receive DAT risk feedback) will include a subset of 10 older adults (65+) drawn from the Stage I Needs Assessment, all of whom have available neuropsychological performance information, magnetic resonance imaging (structural) information, positron emission tomography (PET) amyloid and/or tau information, and apolipoprotein e genetic information already collected as part of UM-MAP, STIM, or DAPPER. Participants will meet all of the inclusion/exclusion criteria applicable for Stage I. Additionally, participants must be negative for mood or anxiety diagnosis and negative on mood measures prior to enrollment in Stage II. Participants must also be currently followed by a medical provider (primary care physician, geriatrician, family doctor). These additional inclusion criteria minimize the likelihood of significant psychological risks following feedback, and facilitate clinical coordination of care between study staff and clinical providers in the event that significant psychological distress does occur.

Co-Participants (those who are currently serving as a caregiver to the participant, or would hypothetically serve in this role should the need arise) include 10 adults, age 18+ years. Similarly, participants must meet criteria from the Stage I Needs Assessment. Additionally, if the participant has

an active legally authorized representative (LAR) or power of attorney (POA) for medical decisions and/or research, that individual must serve in the role of co-participant, and must provide documentation of this legal designation prior to enrollment of the dyad in the study. If the participant does not have an enacted LAR/POA, any individual meeting the above criteria can serve as the co-participant.

All study-related activities will occur at the University of Michigan through virtual visits.

SECTION 3.2 Recruitment Strategy

3.2.1 Stage I: Participants will be recruited from UM-MAP, STIM, or DAPPER. The MADRC recruits participants from several sources including the MADRC Memory Disorders clinic, community screening events, and external referrals. UM-MAP, STIM, or DAPPER participants interested in research are maintained in an IRB-approved database, which is available by request to the PI and her study team.

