Preliminary Screening: Following study team review of the participant's and co-participant's medical record to ensure no interim changes make either part ineligible, the study team will also access the participant's prior MADRC study involvement to determine whether they have adequate information for risk disclosure. Specifically, the study team will communicate with the MADRC UMMAP, STIM, and DAPPER teams to determine if the participant has (a) complete cognitive testing and research diagnosis and (b) recent (within 12 months) data for at least one additional biomarker, including MRI Neuroquant reports, PET amyloid and tau, or APOE genetic results. If the participant meets these criteria, the study team will send an email introducing the study (see 'SHARE(D)' Stage II Email Script') and begin contacting the participant via phone (see 'SHARE(D)' Stage II Oral Script').

Informed Consent for Virtual Visits: The informed consent document will be emailed to participants and co-participants at the time of scheduling, to provide the recipient enough time to review the document. Prior to other study activities, a study team member will set up a phone call or video session to review the consent paperwork together. At this phone appointment, a study team member will explain each section of the informed consent document, pausing to answer questions or clarify misunderstandings. The study team member will also use the Consent Decision-Making Capacity Tool to ensure that the individual providing consent is able to fully understand the decision they are making prior to providing consent. After the informed consent document has been reviewed, eligible participants/co-participants will be asked to provide electronic signature on this form. This can be completed through two methods: (a) the patient can download, sign, scan, and email the form back to the study team member, who will additionally sign as witness and study representative, or (b) the Signnow platform will be used to provide electronic consent. SignNow is a secure platform offered through University of Michigan, which is HIPAA-compliant and approved by Health Information Technology Services (HITS). A copy of the form, with all signatures, will be emailed to the participant/co-participant. Only following receipt of this informed consent document will actual biomarker data be requested and received from the parent study teams (UMMAP, STIM, DAPPER) for integration into the disclosure protocols.

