Additional Screening & Scheduling: Following receipt of the signed informed consent documents, both the participant and co-participant will be asked to complete the GDS-15 and BAI via phone or video (these can be conducted on the same call used to complete the consent documentation). Any individuals who score above the cutoffs for these measures will be ineligible to take part in the study, per eligibility criteria noted above. Additionally, all co-participants must be cognitively intact based on screening or recent evaluation. Co-participants who do not have recent screening or cognitive testing in their medical/research records will be asked to complete a brief phone or video screen (the Blind version of the Montreal Cognitive Assessment [MoCA]) on this call. Co-participants whose scores fall below the cutoff for impairment will be considered ineligible for study participation. Their respective

Figure 3. SHARE(D) Stage II Timeline of Activities

participants will also be asked to delay scheduling of their virtual visit until they can identify another interested and eligible co-participant. Once this secondary screening of the dyad has been completed, the study team will schedule all three sessions for each subject.

Session Description:

Education & Disclosure Session:

During this session, participants and co-participants will complete the following steps, summarized in Table 2:

1. Educational Module – participants and co-participants will be shown an interactive presentation covering the following topics:
 - a. Alzheimer’s disease
 - b. Dementia-Alzheimer’s Type
 - c. Available treatments for AD/DAT
 - d. Available biomarkers or indicators of DAT risk: how they are collected, what information is shared, and what the meaning of this information is relative to risk for AD and DAT
 - e. Risks of learning one’s personal DAT biomarker status
 - f. Benefits of learning one’s personal DAT biomarker status

This module will include multiple opportunities for either member of the dyad to ask questions.

2. Disclosure Preferences & Decision-Making Capacity Assessment – The educational module contains several ‘checks for understanding’ after each section to determine whether the participant fully demonstrates decision-making capacity for risk disclosure. As

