Comprehension and recall of personal risk disclosure information will be measured as accuracy scores on a series questions about the patient's results and the meaning of different messages provided during feedback in regards to AD/DAT risk (i.e., "My Attention was [Normal/Impaired/Don't Know]"). The questionnaire will result in two scores: a Personal Information score and a Meaning of Information score (as it is possible that an individual may accurately remember his/her own information, but misinterpret it, or may understand the meaning of risk information, but incorrectly recall his/her own feedback).

Psychological reactions to personal risk disclosure information will be measured both in terms of general mood and anxiety, as well as feedback-specific distress.

Depression: Mood will be assessed using the self-administered Geriatric Depression Scale – Short Form (GDS-15)³²⁻³³. The GDS-15, a 15-item assessment of depressive symptoms, has been adapted to remove common depression symptoms often conflated with normal aging (i.e.,

somatic symptoms). It asks the participant to rate the presence of mood symptoms over the past two weeks.

Anxiety: The BAI³⁴, also validated for use with older adults³⁵ is a 21-item measure of the perceived severity ('not at all' to 'severely') at which the participant is experiencing anxiety symptoms over the past week.

Feedback-Specific Distress: We will utilize a revised version of the Impact of Genetic Testing for Alzheimer's Disease (IGT-AD) Scale, which itself is based on The Impact of Event Scale (IES)³⁶. The scale will be specifically anchored to the 'life event' of receiving feedback; responses will be slightly modified to assess the impact of receiving any and all AD indicator results (not solely genetic information). The IES and IGT-AD have been utilized to measure test-related distress in previous risk disclosure studies³⁷⁻³⁹, including REVEAL. Participants who have a negative score of 24 or more will be contacted by PI for follow-up with participant/co-participant.

Exploratory Outcomes

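### The Stage II mood and anxiety screen has no maximum interval to disclosure and no repeat before it, so an elevation arising in between would first be seen after results are given

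*Combined protocol and SAP*

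**What the plan says.** Section 3.1.2 requires Stage II participants to be "negative on mood measures prior to enrollment in Stage II", and gives the purpose: "These additional inclusion criteria minimize the likelihood of significant psychological risks following feedback". Section 3.3.2 (Additional Screening & Scheduling) has both members of the dyad complete the GDS-15 and BAI once the signed consent is in, and states: "Any individuals who score above the cutoffs for these measures will be ineligible to take part in the study". On timing it adds that "these can be conducted on the same call used to complete the consent documentation".

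The later steps are also in 3.3.2. On data: "Only following receipt of this informed consent document will actual biomarker data be requested and received from the parent study teams". On scheduling: "Once this secondary screening of the dyad has been completed, the study team will schedule all three sessions for each subject". If the co-participant fails the cognitive screen, the participant is asked to hold off scheduling until another eligible co-participant is found, and no limit is set on that wait.

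Within the disclosure session, the numbered steps and Table 2 run from education through preferences and decision-making capacity to disclosure. Outcome measures and the psychologist's risk assessment follow disclosure. Section 4.1.2 says that the GDS-15 and BAI are repeated at this session and at 1 and 6 weeks. The GDS-15 asks the person to "rate the presence of mood symptoms over the past two weeks"; the BAI concerns "experiencing anxiety symptoms over the past week". Section 3.4.2.2 summarises the scores under Outcome 2.2 and calculates change from the Stage I scores.

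**The concern.** The criterion is tied to enrollment, whereas the risk it is meant to reduce arises at disclosure. Between the two lie a data request, personalization of the protocol, scheduling and possibly the search for a new co-participant. Someone whose mood or anxiety worsens in that time still counts as eligible, and no scheduled measure would show it before results are given.

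Two things are at stake. The first is the protection that the criterion is meant to give. The second is interpretation. Psychological distress is a Stage II primary outcome, the design has a single group, and no required score describes the person just before disclosure. An elevation that preceded disclosure could therefore be reported as a reaction to it, or could make the attribution step in section 4.3 harder to carry out.

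**Working it through.** The plan gives no figure to reproduce: Stage II is descriptive, with no power or alpha statement. The check is of the order of steps, then of the look-back windows, then of scale.

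**Order of steps**

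1. Consent is signed (3.3.2, Informed Consent).
2. GDS-15 and BAI screen, possibly on the same call (3.3.2, Additional Screening & Scheduling).
3. Biomarker data are requested after consent; the three sessions are scheduled after the dyad's screening. There may be a wait for a replacement co-participant.
4. Education module, preferences, capacity assessment, disclosure (3.3.2; Table 2, items 2 to 5).
5. Next GDS-15 and BAI (3.3.2, step 4; Table 2, item 9; 4.1.2).

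No interval is given between steps 2 and 4, and no mood measure is listed within step 4 before disclosure. The plan does set times elsewhere: Stage I sessions follow telephone screening by about one week (3.3.1), and Stage II biomarker data must be within 12 months (3.3.2, Preliminary Screening).

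**Look-back windows**

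For a scale with a window of w days, rated t days after disclosure, the share of the window lying before disclosure is max(0, w − t)/w.

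| Rating | GDS-15 (w = 14) | BAI (w = 7) |
|---|---|---|
| Immediately after (t = 0) | 14/14 = 100% | 7/7 = 100% |
| 1 week (t = 7) | 7/14 = 50% | 0% |
| 6 weeks (t = 42) | 0% | 0% |

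The immediate scores thus refer almost entirely to days before disclosure, and half of the 1-week GDS-15 window does too.

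**Scale**

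The documents give neither the length of the gap nor the rate of new elevations. Let p be the assumed chance that one person newly crosses a cut-off between screen and disclosure, treated as independent across people. The expected number among 20 is 20p, and the chance of at least one among n people is 1 − (1 − p)^n.

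| Assumed p | Expected among 20 | At least one of 20 | At least one of the 10 participants |
|---|---|---|---|
| 1% | 0.2 | 1 − 0.99^20 = 18% | 10% |
| 2% | 0.4 | 1 − 0.98^20 = 33% | 18% |
| 5% | 1.0 | 1 − 0.95^20 = 64% | 40% |

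One person in 20 adds 1/20 = 5 percentage points to any reported proportion above a cut-off.

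**Baseline**

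Section 3.4.2.2 measures change from Stage I. A fresh Stage II screen alone would leave the change score carrying everything that happened since Stage I, so the baseline must change as well.

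**The case against.** The strongest reply is that the screen is one safeguard among several. Participants must have no mood or anxiety diagnosis and must have a medical provider (3.1.2). Records are reviewed before contact (3.3.2). A licensed psychologist is available at every session (4.2), and other signs of new or worsened mood symptoms also trigger evaluation (4.1.2). The biomarker data already exist, so the gap may be short, and Figure 3, which shows the Stage II timeline, is not available to read. The distress scale is anchored to the feedback event, and section 4.3 asks whether changes are attributable to participation. Stage II is a descriptive pilot of 20 people.

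All of this stands, and it limits the point without removing it. None of these safeguards is a scheduled mood measure before disclosure, and the wait for a replacement co-participant is open-ended. An interval printed only in Figure 3 cannot be ruled out, but the governing text should state it. The attribution step has no score from just before disclosure to draw on.

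A reader might infer that a screen older than the look-back period is uninformative, or that the criterion cannot work as timed. The documents do not support this: an older screen remains partly informative, and section 3.1.2 claims only to reduce the likelihood of harm. Nor is it certain that an earlier elevation would be read as a reaction, since the look-back windows themselves give reason for caution with the immediate scores.

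**Conclusion.** The point holds for the readable text. Followed exactly, the plan allows a GDS-15/BAI screen of any age to stand at disclosure, with the next scores taken only after results are given. An elevation arising in between could be counted in Outcome 2.2 or complicate adverse event attribution. This concerns the GDS-15 and BAI more than the event-anchored distress scale.

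The size is unknown. The 18-64% chance of at least one such person among 20 rests wholly on an assumed 1-5% rate and on independence, which members of a dyad may not satisfy. No test or power calculation is affected. The change is worth making because psychological distress is a primary outcome, there is no control group, and the screen is part of the plan's stated protection.

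**What to change.** - **Section 3.3.2 and Table 2:** state a maximum interval from the qualifying GDS-15 and BAI to the disclosure session. When the screen is older, give both scales before the education module or shortly before the session. The study team should set the interval with reference to the scales' look-back periods.
- **Sections 3.1.2 and 3.3.2:** reconcile how the existing eligibility criterion, now tied to enrollment, applies to that later score.
- **Section 3.4.2.2:** use the latest pre-disclosure score, not the Stage I score, as the baseline for GDS-15 and BAI change. Because the look-back windows overlap, the immediate change should still be read with care.

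The cost is a few sentences of text, a short repeat of two questionnaires for delayed dyads, and possibly a postponed session.

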3.4.1 Data Management & Entry

Only IRB approved study personnel will have access to study documents/data. Signed consent paperwork and will be uploaded into the participant's medical record according to IRB standards and then stored in a binder, separate from all other study data. Electronic consent forms will be saved under password protection on the secure lab drive. Copies will be printed and stored in the aforementioned binder, away from all other study data. Data are kept in a locked file cabinet within a private office in an office suite (i.e., behind two locked doors). The participant's study ID number will be recorded on every paper page of the study documents.

The participants' biomarker data (beyond UM-MAP, STIM, or DAPPER diagnosis) will not be requested or stored as part of this study until completion of Stage I, to ensure no implicit bias in the manner in which needs assessment procedures are conducted based on participant risk. At this time, data from the 10 participants enrolled in the Stage II feedback piloting will be requested through the secure UM-MAP, STIM, or DAPPER Data Core avenue; de-identified participant information, coded with the UM-MAP, STIM, or DAPPER ID number, will be shared with the study team as a secure excel database. This file will reside on the University of Michigan secure server as a password protected file only accessible by approved study personnel.

3.4.2 Statistical Design

Data Screening (Stage I & II)

Prior to statistical analyses, data screening will be conducted. Initial steps will include a missing data analysis to determine randomness of missing data and range checks to assess for data quality. Additional screening for univariate and multivariate outliers, skewness and kurtosis will be conducted to inform needs for data transformation and statistical approach. Additionally, for Stage I data, we will compare outcomes in participants who completed in-person vs. video vs. phone visits to ensure that session modality did not impact interpretation of results.

Statistical Approach

